---

## 1 ABBREVIATIONS USED IN THE PROTOCOL

| Abbreviation | Term   |
|---------------------|---|
| ACE                 | Angiotatin-converting enzymes                       |
| AE                  | Adverse Event                                       |
| ARB                 | Angiotensin Resistant II Blockers                   |
| CFR                 | Code of Federal Regulation                          |
| CRT                 | Cardiac Resynchronization Therapy                   |
| EHR                 | Electronic Health Record                            |
| GCP                 | Good Clinical Practice                              |
| GIRB                | Geisinger Institutional Review Board                |
| HBP                 | His-Bundle Pacing                                   |
| HIPAA               | Health Insurance Portability and Accountability Act |
| HOT-CRT             | His-Optimized Cardiac Resynchronization Therapy     |
| IRB                 | Institutional Review Board                          |
| LBB                 | Left Bundle Branch                                  |
| LBBP                | Left Bundle Branch Area Pacing                      |
| LV                  | Left Ventricular Pacing                             |
| NYHA                | New York Heart Association                          |
| PHI                 | Personal Health Information                         |
| RVP                 | Right Ventricular Pacing                            |
| SAE                 | Serious Adverse Event                               |
| WHO                 | World Health Organization                           |

## 2 BACKGROUND AND SIGNIFICANCE

Physiologic pacing has become rapidly accepted into clinical practice. His bundle pacing (HBP) has recently been incorporated into Guideline document for bradycardia pacing. Advances have been made in physiologic pacing in the form of left bundle branch area pacing (LBBAP). Recent report by Huang et al described a novel approach to implanting the Medtronic 3830 lead in the Left bundle branch area via right ventricular, deep septal approach. Early experience suggests that LBB pacing can result in significant improvement in LV function in patients with LBBB and heart failure. The potential advantage of this method is several fold: 1. Bypass the site of conduction block in patients with LBBB (even in patients where His bundle pacing fails to correct the LBBB) 2. Achieve low capture threshold with excellent sensing 3. Obtain LV

## CONFIDENTIAL AND PROPRIETARY

---

endocardial pacing in addition to conduction system pacing without a lead in the LV endocardial cavity.

The electrophysiological and ECG characteristics of LBB Pacing has not been well described. The ECG Belt can help assess the difference between baseline, RV pacing, LBBAP and His (or LBBAP) Optimized CRT (HOT-CRT) and understand the electrical synchrony and characteristics of physiologic pacing.

### **3 OBJECTIVES**

#### **3.1 General Objective**

The objective of the study is to assess the utility of ECG Belt to understand the conduction and ECG characteristics of LBBAP and HOT-CRT and compare with preexisting data in traditional CRT and RVP.

#### **3.2 Specific Objective**

- To demonstrate and establish electrical resynchronization using ECG Belt Research System in LBBP and HOT-CRT.
- To assess ECG Belt derived native conduction parameters and compare them to LBBAP and HOT-CRT.
- To compare with historic ECG belt parameters obtained for right ventricular pacing/ Biventricular pacing in prior studies (Bank et al)

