#### **4.6 Primary Endpoints**

The primary endpoints will be

- ECG Belt analysis of Standard Deviation of Activation Times (SDAT) of LBBAP compared to native conduction
- ECG belt analysis of Left Ventricular activations times (LVAT) of LBBAP compared to baseline
- ECG belt analysis of SDAT and LVAT of HOT-CRT compared to baseline
- ECG belt analysis of QRS duration at baseline compared to various LBBAP options
- Comparison of above parameters of LBBP to historic biventricular or RV pacing

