#### **4.8 Statistics**

Summary tables of descriptive statistics will be provided for all variables. Continuous variables will be summarized using means and standard deviations or median and interquartile ranges (IQR), depending on distributional assumptions. Categorical variables will be summarized using percentage and frequency counts. The descriptive statistics will be reported for Baseline and follow-up (adverse events only will be collected).

Analysis of the following objectives will be accomplished using the Chi-square or Fisher's exact tests, and T-tests or non-parametric test (Median test, Wilcoxon rank sum test, etc.), as appropriate.

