**CONFIDENTIAL AND PROPRIETARY**

- 
- To assess ECG Belt derived native conduction parameters and compare them to LBBAP and HOT-CRT.
    - ECG Belt analysis of Standard Deviation of Activation Times (SDAT) of LBBAP compared to native conduction
    - ECG belt analysis of Left Ventricular activations times (LVAT) of LBBAP compared to baseline
    - ECG belt analysis of SDAT and LVAT of HOT-CRT compared to baseline
  - These ECG belt characteristics will be compared with historic ECG belt parameters obtained for right ventricular pacing/ Biventricular pacing in prior studies

This study is information gathering and not designed to perform any hypothesis testing. Therefore, any results of statistical tests performed are not conclusive but used to design a larger prospective study.

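### Specific objective 1 sets out to establish electrical resynchronization, which conflicts with section 4.8, and it is tied to no named analysis and no criterion

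*Combined protocol and SAP*

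**What the plan says.** Section 3.2 lists three specific objectives. The first is "To demonstrate and establish electrical resynchronization using ECG Belt Research System in LBBP and HOT-CRT". The second compares native conduction parameters with LBBAP and HOT-CRT. The third compares with historic belt data.

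The general objective in 3.1 is milder: "The objective of the study is to assess the utility of ECG Belt to understand the conduction and ECG characteristics of LBBAP and HOT-CRT".

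Three of the primary endpoints in 4.6 concern SDAT and LVAT against the patient's own reference. The first of these reads "ECG Belt analysis of Standard Deviation of Activation Times (SDAT) of LBBAP compared to native conduction". Next, for the other measure in the same pacing mode, comes "ECG belt analysis of Left Ventricular activations times (LVAT) of LBBAP compared to baseline". For the optimized resynchronization systems, the plan has "ECG belt analysis of SDAT and LVAT of HOT-CRT compared to baseline". None has a threshold. There are no secondary endpoints (4.7).

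Section 4.8 opens its list of analyses with "Analysis of the following objectives will be accomplished using the Chi-square or Fisher's exact tests, and T-tests or non-parametric test". It gives the median test and the Wilcoxon rank sum test as examples of non-parametric tests, and adds that the choice will be made as appropriate. The list then holds objective 2, with the three SDAT and LVAT comparisons beneath it, and the historic comparison. The section closes with "This study is information gathering and not designed to perform any hypothesis testing" and says that test results will serve to design a larger study.

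**The concern.** Objective 1 is the one specific objective worded as a confirmatory claim. Section 4.8 says the study is not built to deliver such a claim, does not name the objective among those to be analysed, and gives no rule by which a reader could tell whether it was met.

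What is at stake is the report. Section 7 plans an abstract and a peer-reviewed manuscript. With 3.2 and 4.8 as they stand, one author could point to the objective and report a nominal p-value as resynchronization established, while another could point to 4.8 and say that no such conclusion is allowed. The protocol should not license both.

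**Working it through.** The documents give no alpha, power, effect size, SD, threshold or sample-size derivation, so there is no figure of the plan's own to reproduce. The check is mainly a comparison of the text.

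**Step 1. Trace each specific objective to 4.8.**

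| Objective (3.2) | Named in the 4.8 list? | Endpoints in 4.6 that bear on it |
|---|---|---|
| 1. Resynchronization in LBBP and HOT-CRT | No | SDAT and LVAT of LBBAP and HOT-CRT against native conduction or baseline |
| 2. Native conduction against LBBAP and HOT-CRT | Yes, with three sub-items | The same comparisons |
| 3. Historic comparison | Yes | Comparison with historic biventricular or RV pacing |

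Section 2 presents the belt as a way to understand electrical synchrony. The SDAT and LVAT comparisons are therefore the substance of objective 1, although they are filed under objective 2.

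**Step 2. Look for a criterion.** Sections 3, 4.6 and 4.8 give no cut-off, minimum change or responder rule. Section 4.2.2 admits bradycardia as well as heart failure indications and requires no dyssynchrony at baseline. It is therefore not self-evident what resynchronization would mean in every patient.

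**Step 3. Compare the strength of the claims.** Section 3.1 aims to assess and understand. Section 4.8 gathers information and disclaims conclusions. Objective 1 aims to demonstrate and establish. Two of the three agree, and objective 1 is the exception.

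**Step 4. Match the named tests to the data.** Under 4.5, each patient is recorded in native conduction and in the paced modes at the same visit, so these comparisons are within-patient. The rank sum and median tests named in 4.8 are for independent samples.

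**Step 5. What the study can deliver (illustration).** The 95% CI half-width for a mean within-patient change, in units of the SD of that change, is t(0.975, n−1)/√n.

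| n | t | √n | Half-width |
|---|---|---|---|
| 20 | 2.093 | 4.472 | 0.47 SD |
| 15 | 2.145 | 3.873 | 0.55 SD |
| 10 | 2.262 | 3.162 | 0.72 SD |
| 5 | 2.776 | 2.236 | 1.24 SD |

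Only the approximate total of 20 (4.2.1) comes from the documents; the smaller values of n are assumptions. With 20 patients, an observed mean change above 0.47 SD would have an interval that excludes zero. That shows a change. Without a criterion it does not show that resynchronization has been established.

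**The case against.** The strongest reply is that one strong phrase in one bullet does not make a study confirmatory. The general objective is descriptive, and 4.8 states plainly that results are not conclusive, so a careful author is already warned. This stands in part. It limits the importance of the point, but it does not remove the conflict between 3.2 and 4.8.

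A second reply is that the reworded objective would come close to objective 2. That is largely true, because the same comparisons serve both. What the rewording adds is a named quantity and an explicit link to the endpoints.

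A reader might infer several stronger things that the documents do not support:

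- *That no listed analysis addresses objective 1.* The SDAT and LVAT comparisons in 4.6 and 4.8 address it in substance. What is missing is the mapping and a criterion.
- *That the study cannot support its aims.* This holds only if objective 1 is read as confirmatory. Estimating within-patient change is feasible and fits 3.1 and the stated purpose of planning a larger study.
- *That HOT-CRT will have far fewer patients.* Section 4.2.1 gives no split, and two of the three eligible systems in 4.2.2 (LBBAP+LV lead and HBP+LV) are of the HOT-CRT type.
- *That the chi-square and Fisher tests must be deleted.* All the endpoints in 4.6 are continuous, but 4.8 applies tests only where appropriate. Tests without a categorical endpoint would simply go unused.
- *That counting patients whose SDAT falls would supply the criterion.* Such a count includes any fall, however small. It is descriptive and does not define resynchronization.

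**Conclusion.** The point holds as a conflict of wording and a gap in traceability. Objective 1 claims more than 4.8 allows, is the one of three specific objectives not named there, and has no stated result that would meet it. The study can estimate the change in SDAT and LVAT; it cannot establish resynchronization.

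The defect is modest. The study is openly exploratory, the relevant measurements are already planned, and the disclaimer in 4.8 is explicit. The interval widths do not measure the defect and would be the same after the fix; they show only the precision to expect. They assume a paired t interval at the 95% level, and below 20 they rest on assumed patient numbers. I read baseline in 4.6 as the same reference as native conduction.

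**What to change.** 1. In 3.2, restate objective 1 along these lines: *to estimate the within-patient change in SDAT and LVAT from native conduction during LBBP and during HOT-CRT*. Since 4.6 uses both native conduction and baseline, say that they are the same reference, or define each.
2. In 4.8, name objective 1 and map it to the existing SDAT and LVAT primary endpoints.
3. In 4.8, make the main result for these endpoints the mean (or median) within-patient change with its SD and 95% CI, given separately for LBBAP and HOT-CRT with the number of patients in each. This replaces independent-sample tests for the within-patient comparisons; the historic comparison is a separate matter.
4. If the number of patients with a fall in SDAT is also reported, label it descriptive.

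The cost is a few sentences in 3.2 and 4.8, slightly more analysis, and a less favourable stated claim. No patients, visits or recordings are added. The gain is that 3.1, 3.2 and 4.8 agree, and that the report gives the size and spread of the change, which the planned larger study will need.

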### **4 STUDY DESIGN**

#### **4.1 Description**

The ECG Belt study is a prospective, single-center, investigational, pre-market research study. The study team will identify all patients who satisfy the inclusion and exclusion criteria. The study team will evaluate the ECG Belt Research System to assess the electrical characteristics of conduction system pacing in patients with preexisting LBBAP or HOT-CRT.

### **CONFIDENTIAL AND PROPRIETARY**

---

Eligible patients would have successfully undergone LBBAP using Medtronic 3830 lead and C315His sheath. LBBAP will be confirmed at implant using left bundle potentials recorded from the lead, ECG morphology during unipolar and bipolar pacing, peak LV activation time and lead depth in the LV septum by contrast at implant and 2D echo post-implant.

ECG belt would be used to record ECG during baseline rhythm, LBBAP in unipolar and bipolar configurations and / or during HOT-CRT using HBP or LBBAP. These ECG belt characteristics would then be compared with baseline and existing data on RV pacing and traditional Biventricular pacing.

## **4.2 Study Population**

### **4.2.1 Approximate Number of Subjects**

Approximately 20 patients will participate in the ECG Belt study to be conducted at Geisinger Heart Institute.

All patients will share the same recruitment process, inclusion and exclusion criteria and same procedures.

### **4.2.2 Inclusion Criteria**

The following is the inclusion criteria for the ECG Belt study:

1. Patients > 18 years of age
2. Patient has a previously implanted LBBAP lead for bradycardia indication or heart failure indication with one of the following at Geisinger within the last 5 years:
  - LBBAP
  - LBBAP+LV lead
  - HBP+LV
3. Patient is willing to comply with all study procedures and be available for the duration of the study.

#### **4.2.3 Exclusion Criteria**

The following patients or situations are excluded in the ECG Belt study:

1. Inability to provide informed consent
2. Pregnant
3. Enrolled in a concurrent study that may confound the results of this study.

#### **4.3 Recruitment**

Potential participants will be identified by clinician referrals, or by review of the electronic health record (EHR) of patients. Research staff will contact potential subjects and invite them to participate.

#### **4.4 Study Duration**

##### **4.4.1 Approximate Duration of Subject Participation**

Subjects will participate in the study for approximately 1 week (+/- 5 days). This includes a monitoring (follow up) period which starts immediately after signing the Informed Consent and completing the baseline visit (visit 1).

##### **4.4.2 Approximate Duration of Study**

This study will be completed in approximately 12-15 months duration. The end of the ECG Belt study is the completion of data entry and statistical analysis.

This study duration approximation is composed of the following stages:

- Screening and Enrollment Stage – enrollment of 20 patients from Geisinger Heart Institute is expected to take 10-12 months based on enrollment rate of 1 to 2 subjects per month.
- Monitoring Stage – based on the planned 1 week monitoring period for each patient, last patient completed is expected 10-12 months from the study beginning.

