**CONFIDENTIAL AND PROPRIETARY**

- 
- Data Collection Stage – data entry and management are ongoing leveraging the electronic data capture system and secured database.
  - Statistical Processing and Data Analysis – is expected to take 1-3 months from the data entry of the last patient visit or the last patient enrolled.

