## 4.5 Procedures

The ECG Belt study methodology is composed of:

- 1 scheduled clinic visits (baseline)
- 1-week follow-up monitoring period for adverse events (phone call).

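### Does the 10-12 month enrolment forecast, which does not follow from 1 to 2 patients per month, require a change to the plan?

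*Combined protocol and SAP*

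**What the plan says.** Section 4.2.1 sets the size: "Approximately 20 patients will participate in the ECG Belt study". Section 4.4.2 builds a timeline on that number. It refers to "enrollment of 20 patients from Geisinger Heart Institute" and says that this "is expected to take 10-12 months based on enrollment rate of 1 to 2 subjects per month". The monitoring stage repeats the range: "last patient completed is expected 10-12 months from the study beginning". The analysis stage, listed last in the same section, "is expected to take 1-3 months from the data entry of the last patient visit". The total at the head of the section is "This study will be completed in approximately 12-15 months duration".

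The same section defines when the study is over: "The end of the ECG Belt study is the completion of data entry and statistical analysis". That is an event, not a date. Section 4.4.1 puts each participant's involvement at about one week, give or take 5 days. Section 4.1 describes a single-center study, and section 4.8 says that the study gathers information and is not designed for hypothesis testing.

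**The concern.** The enrolment sentence presents the months as a consequence of the rate, so a reader can divide one by the other, and the division fails at the upper end. The difference is not rounding: 12 months are stated, and the slowest stated rate gives 20. Nothing else in the documents accounts for the 12. No second site is planned, no other rate is given, and no start-up period is described (one would lengthen enrolment, not shorten it).

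The 12 months also carry into two further forecasts, time to last patient completed and total duration, so one line affects three figures. If accrual ran at the slow end of the stated range, the study would run well past its stated 15 months. In a trial with a fixed calendar stop, that could mean a smaller sample, less precise estimates or unplanned pressure to close early. That possibility is what makes the discrepancy worth checking.

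**Working it through.** **Inputs**

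- Patients to enrol: N = 20 (sections 4.2.1 and 4.4.2).
- Rate: r = 1 to 2 per month (section 4.4.2).
- Follow-up: 1 week (section 4.4.1), or 7/30.44 = 0.23 month.
- Analysis: 1 to 3 months (section 4.4.2).

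**Enrolment time = N / r**

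| Rate per month | Months to enrol 20 | Enrolled by month 12 |
|---|---|---|
| 2 | 20/2 = 10.0 | all 20 |
| 1.5 | 20/1.5 = 13.3 | 12 × 1.5 = 18 |
| 1 | 20/1 = 20.0 | 12 × 1 = 12 |

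The stated lower end of 10 months is reproduced. The stated upper end of 12 is not. Solving backwards, 10 months needs 20/10 = 2.0 per month and 12 months needs 20/12 = 1.67. The stated months therefore fit only rates of 1.67 to 2, the fastest third of the stated range: (2 − 1.67)/(2 − 1) = 0.33.

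**Total = enrolment + follow-up + analysis**

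- With the plan's own 10-12 months: 10 + 0.23 + 1 = 11.2 up to 12 + 0.23 + 3 = 15.2. The stated total is 12-15. The upper end matches, so the 15 is built on the 12. The lower end is a little below the stated 12, within what an approximate figure allows.
- At 1.5 per month: 13.33 + 0.23 + 1 = 14.6 up to 13.33 + 0.23 + 3 = 16.6. This overlaps the stated range and passes its upper end by about 1.6 months.
- At 1 per month throughout, with the longest analysis time: 20 + 0.23 + 3 = 23.2. Last patient completed would be at 20 + 0.23 = 20.2 months.

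**Where the forecast is used**

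- Sample size: stated directly as about 20 in section 4.2.1, not derived from a rate or a period.
- End of study: completion of data entry and analysis (section 4.4.2). Slow accrual moves the date and cuts nothing off.
- Primary endpoints (section 4.6): ECG Belt measurements from the single baseline visit, compared with native conduction or baseline and with historic data. None involves calendar time.
- Statistics (section 4.8): descriptive summaries and exploratory tests, with no interim look, calendar cut-off or decision rule.
- Safety (section 5): adverse events related to the ECG Belt, followed for about a week per participant. No rule depends on how fast patients enter.

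The forecast feeds into none of these.

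**The case for a change.** The best case for a correction is that the error is certain and cheap to remove. The months are offered as derived from the rate and they are not. Words such as approximate and expected can absorb rounding, but not 12 against 20, and even the middle of the rate range overshoots 12. Restating the rate as about 1.7 to 2 per month would change one figure. Keeping the rate and lengthening the upper ends would change three. Because the study ends by event, slow accrual within the stated range really would extend it, and someone planning resources from section 4.4.2 could be misled.

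The arithmetic in that case stands, and nothing in the documents reconciles the figures. The consequence does not. Twenty months needs an average of only 1 patient per month over the whole period, and 23 months adds the longest analysis time; these are worst-case bounds, not forecasts. An average of 1.67 to 2 per month lies inside the stated range, so 10-12 months can be an honest expectation badly matched to its stated rate. The text does not say that this was meant, and the documents do not show whether the rate or the months is the slip. The documents base no staffing, equipment or ethics-renewal plan on this section, so harm of that kind would be supposition. The event-based ending also works in the plan's favour: late accrual costs time, not patients or data.

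**Conclusion.** The rate and the months in section 4.4.2 disagree at the upper end: 12 months stated for enrolment against 20 at the slowest stated rate, a gap of 8 months. The same slip sits behind the upper ends for last patient completed (12 stated, about 20 at worst) and total duration (15 stated, about 23 at worst). At 1.5 per month the overrun is much smaller, about 1.3 months for enrolment and 1.6 for the total.

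This is a clerical inconsistency in a forecast, and no change to the plan follows. The target of about 20 patients, the endpoints, the analysis and the safety follow-up are the same whichever figure was intended, and a reader who needs a timeline can redo the division at once.

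The conclusion rests on three features of the documents: a sample size not tied to a calendar period, an ending by event, and no analysis or rule that refers to accrual. The calculations assume a constant rate and a one-week follow-up; the longest allowed follow-up, 12 days, adds 5/30.44 = 0.16 month to the one-week figures and makes no material difference.
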